13.2 Assessing Severity of Adverse Events

The severity of AEs will be designated by the investigator as mild (Grade 1), moderate (Grade 2), severe (Grade 3), life-threatening (Grade 4), or fatal (Grade 5),

Adverse Event Severity

Grade	Definition
Mild – Grade 1	Mild; asymptomatic or mild symptoms; clinical or diagnostic observations only; intervention not indicated
Moderate – Grade 2	Moderate; minimal, local or noninvasive intervention indicated; limiting age-appropriate instrumental activities of daily living (ADL) ¹
Severe – Grade 3	Severe or medically significant, but not immediately life threatening; hospitalization or prolongation of hospitalization indicated; disabling; limiting self-care ADL ²
Life-threatening – Grade 4	Life-threatening consequences; urgent intervention indicated
Death – Grade 5	Death related to AE

¹*Instrumental ADL* refers to preparing meals, shopping for groceries or clothes, using the telephone, managing money, etc.

²*Self-care ADL* refers to bathing, dressing and undressing, feeding self, using the toilet, taking medications, and not being bedridden.

13.3 Assessing Relationship of Adverse Event to Study Treatment

All AEs will be categorized by the Investigator with respect to their possible relationship to study treatment. The relationship between study treatment and the AE may be considered related or not related. The criteria for each category are listed below:

- Related: When there is a reasonable possibility that the study treatment caused the reported AE
- Not related: When there is no reasonable possibility that the study treatment caused the reported AE.

13.4 Recording of Adverse Events

All AEs with onset dates after the subject signed the ICF through the 6-month visit will be recorded on the CRF. All AEs must be recorded on the appropriate CRF, regardless of their severity or relationship to the CTM. All AEs that meet the seriousness criteria (Section 13.6) will be recorded as an SAE.

All clinical events are to be recorded, including both observed (such as any reaction at injection sites) and volunteered problems, complaints, or symptoms. The need to capture this information does not depend upon the clinical event's association with the use of the CTM. Adverse events resulting from concurrent illnesses, reactions to concurrent medications, or clinically significant progression of disease states are also to be recorded.

13.5 Adverse Event Recording Period

AEs will be collected and recorded on the CRF from the time the ICF is signed by the subject through the 6-month follow-up visit.

13.6 Serious Adverse Event Definition

A *serious adverse event* (SAE) is defined as any AE occurring at any dose regardless of relationship to CTM that results in any of the following outcomes:

- Death
- Is life-threatening
- Requires inpatient hospitalization or prolongation of existing hospitalization
- Results in persistent or significant disability or incapacity
- Other significant medical events.

In addition, all AEs assessed by the investigator with severity of Grade 4 or Grade 5 should be reported as SAEs. An important medical event that may not result in death, be life-threatening or require hospitalization may be considered an SAE when, based upon appropriate medical judgment, it may jeopardize the subject and may require medical or surgical intervention to prevent one of the outcomes listed above.

Complications that occur during hospitalization are AEs. If a complication prolongs a hospitalization, it is an SAE.

As used in this study, the term *inpatient hospitalization* is defined as formal admission to a hospital for medical reasons or evaluation in the Emergency Department of a hospital even if not admitted.

When an SAE occurs in a subject receiving a product as a concomitant medication, the SAE must be processed and reported.

13.7 Serious Adverse Event Recording Period

The Investigator will collect and record SAEs from the time the subject signs the ICF through the 6-month follow-up visit.

13.8 Regulatory Reporting of Adverse Events

The Investigator will determine whether the SAE must be reported to the FDA within 7 or 15 days, and if so, will report the event to the FDA. The Investigator will report all SAEs to their IRB, as required. Adverse events will be reported to regulatory authorities in compliance with local and regional law and established guidance. The format of the reports will be dictated by local and regional requirements.

13.9 Data Safety Monitoring Board (DSMB)

Acknowledging the inherent vulnerability of our study population (older hemodialysis patients), a DSMB will be established with a mission to ensure that the interests of the patients entered in the trial are being well served (i.e., the risk-benefit ratio is appropriate) and that the scientific integrity of the trial is maintained from trial initiation to completion [21]. The DSMB will be comprised of three independent physicians with expertise in nephrology, geriatric medicine and infectious disease as well as one independent biostatistician. The committee will meet at trial initiation and quarterly for the one-year duration of the study.

The study will be stopped if the DSMB believes that the number or severity of treatment-related adverse events suggests that it is in the best interests of the patients to do so.

14 DATA MANAGEMENT

Data will be entered onto the CRFs. The Investigator should ensure the accuracy, completeness and timeliness of the data recorded on the CRFs.

15 STATISTICAL ANALYSIS

15.1 Sample size justification

It has been speculated that infection rates may be as high as 40% in the general population and for those over the age of 60 years, particularly those with underlying comorbidities, the rate may be higher. Further, patients who receive dialysis two or three times weekly at dialysis centers are more likely to be exposed to virus than the general elderly population. In as much as there are no existing data demonstrating the effects of Ta1 in prevention of COVID-19 infection, in this pilot project we have elected to sample 240 subjects, anticipating that 40 subjects will drop off study for any of a number of reasons. That will leave ~200 enrolled subjects with complete data availability. We justify the choice of sample size below.

Clinical Study Protocol: Ta1 to Prevent COVID-19 Infection in Elderly Renal Dialysis Patients

Each sample size calculation depends on the type of endpoints, the variability of data, analysis methods used, and the minimal difference (or effect size) that we wish to be able to detect between the treatment (with Zadaxin) or control (without Zadaxin) groups. There are four types of endpoints for this study, dichotomous (e.g., infection of COVID19, the primary endpoint; ICU admission; or mortality), polytomous (e.g., health changes: no change, moderate, severe changes), counts (e.g., occurrence of non-COVID-19 infections), or continuous outcome variables (e.g., CD4, CD8, CD4/CD8, length of hospital stay, recovery time from COVID19). For a dichotomous outcome, a suitable model is a logistic regression with the treatment status (treated or not treated with Zadaxin) as the primary covariate, demographic information (age, gender, race), health/medical information (e.g., Karnofsky score, co-morbidity, and other biomarkers) and environmental information (treatment center, among others) as other relevant covariates. Assume the infection rate for the control group is about 0.40 and with a significance level of 0.05 (unless specified otherwise), if we use a simple logistic regression, a sample of size 200 will be able to detect a change at least at 0.185 in the infection rates between the treatment and control groups with a power of 80%. If we have a bigger sample size, say 234, we would be able to detect a change with a minimal difference of 0.17 with the same power or a minimum difference of 0.185 with a power of 86.5%. Using more comprehensive procedures (below) or if the actual difference is (much) larger than the minimal difference, we will have a (much) higher power than 80% to detect the actual difference. If we make a conservative adjustment for multiple comparisons incorporating other covariates after a pre-screening step, at an adjusted significance level 0.005, a sample of size 205 will provide 80% power for detecting a change of at least as large as 0.23. Using a multiple logistic regression model that takes into account the correlation among the various covariates, say if the correlation is 0.2, we can detect a minimal difference at 0.202 with a sample size of 200. If the correlation is 0.5, the minimum detectable difference would be 0.25. The highly correlated covariates that lead to multicollinearity will indicate the need for removal of redundant covariates in modeling the endpoint, and the removal will lead to more degrees of freedom in our study and the same power in detecting the even smaller difference. We will use all the sample we have and incorporate censored data or treat missing information with survival or a more comprehensive model than the logistic regression; thus, we expect to be able to detect a smaller minimal difference or have a much higher power to detect the actual difference in the infection rates than given above.

For a continuous endpoint, with a sample size of 201, using the simplest testing procedure (with a possible transformation of the endpoint variable), we will be able to detect an effect size at least at 0.35 between the treatment and control groups with a power of 80%. Since we will use a general linear model to delineate the effects or variations due to covariates/factors, we expect to be able to detect a smaller minimal effect size or a higher power to detect the actual difference that is bigger than the minimal effect size. In a very conservative sense, comparing a polytomous response between treatment and control can be viewed as a multiple testing problem of comparing proportions for each of the categories. For response variables with three categories, if the proportion of a certain category is approximately 0.3, a sample of size 202 will enable us to detect a minimal change of 0.19 with a power of 80%. We emphasize that this calculation is very conservative, and we expect have much better performance, both in terms of detection of smaller departure and having better power. For the ordinal polytomus outcome, we are interested in

identifying if the treatment improves the proportion of different categories of the outcome than that of control. Assume that the response has 3 categories with equal proportion in the overall population (averaged over control and treatment). With a sample size of 200 we can detect a minimal improvement of size 0.725 in the overall odds ratio with 80% power. The count variables can be modeled as continuous with appropriate transformation and the sample size justification will be similar to that of a continuous response.

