8.2 Secondary Efficacy Endpoints

The secondary efficacy endpoints are:

1. Need for hospitalization
 - This is defined by documentation in the case report form (CRF) of physician referral to hospital for admission
2. Hospital length of stay
 - The number of overnight stays in the hospital, entered into the CRF
3. ICU admission
 - Documentation in the CRF of physician recommendation for ICU transfer.
4. ICU length of stay
 - The number of overnight stays in the ICU
5. Mechanical ventilation
 - Documentation in the CRF of administration of mechanical respiratory assistance and length of time such assistance required
6. Duration of mechanical ventilation
 - Documented in the CRF by physician
7. Recovery time from COVID-19
 - Defined as testing negative, plus the time for full recovery as determined by physician
 - Documented in the CRF by physician
8. Change in any existing comorbidities (e.g., worsening congestive heart failure) or newly diagnosed disease
 - Documented in the CRF by physician
9. Incidence of secondary non-COVID-19 infections (relapses, superinfections and new infections).
 - Documented in the CRF by physician
10. Change in T lymphocyte subsets (CD4, CD8)
 - Samples taken at enrollment, at 8 weeks and at 6 months, or at time of hospital admission if that is required
11. Mortality
 - COVID-19 related, or non-COVID-19 related; documented in the CRF by physician.

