10.5 Method of Assigning Subjects to Treatment

Subjects who meet all inclusion and exclusion criteria will be centrally randomized 1:1 to receive either no treatment or 1.6 mg Ta1 in 1 mL doses to be delivered twice weekly after dialysis (with treatment days separated by at least 2 full days without Ta1 injection), via SC injection for 8 weeks, in accordance with a computer-generated randomization schedule prepared by the Inova Biostatistical core.

Randomization will be stratified by dialysis site.

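### The 80% power quoted for continuous endpoints (effect size 0.35, N=201) matches only a one-sided test, while the section's checkable proportion figures match two-sided tests, and the same N is applied to recovery time, which exists only in infected patients

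*Combined protocol and SAP*

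**What the plan says.** Section 15.1 sets the level for its calculations by assuming a control infection rate of about 0.40 "with a significance level of 0.05 (unless specified otherwise"). It does not say whether tests are one-sided or two-sided, and neither does section 15.2.

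For the primary endpoint, "a sample of size 200 will be able to detect a change at least at 0.185 in the infection rates" with 80% power. Further figures follow for N=234 and for a level of 0.005.

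For the continuous class the text reads "For a continuous endpoint, with a sample size of 201, using the simplest testing procedure", and then "we will be able to detect an effect size at least at 0.35 between the treatment and control groups with a power of 80" per cent. Covariate modelling by a general linear model is presented as a further gain on top of this figure. Count variables are said to have a similar justification.

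The class is defined earlier in the same section as "continuous outcome variables (e.g., CD4, CD8, CD4/CD8, length of hospital stay, recovery time from COVID19"). Section 8.2 describes recovery time (secondary endpoint 7) as follows: "Defined as testing negative, plus the time for full recovery as determined by physician". It describes hospital length of stay as a number of overnight stays.

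Patients "will be centrally randomized 1:1" (section 10.5). Of 240 enrolled, the plan is "anticipating that 40 subjects will drop off study for any of a number of reasons", which leaves about 200 with complete data.

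**The concern.** There are two separate difficulties. First, 80% power at 0.35 SD with about 100 patients per arm is better than a two-sided 0.05 test delivers, and no change of sidedness is announced between the binary and the continuous calculations. A reader would assume one convention for the whole section and take the continuous endpoints to be better powered than they are.

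Second, one N, essentially every evaluable patient, serves the whole continuous class. Recovery time from COVID-19 has no value in a patient who was never infected, so its denominator is the number infected and not 201.

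At stake is how the secondary results are read. A non-significant difference in recovery time means little if power was about one in four to one in three, but the plan as written lets it be set against a claimed 80%.

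**Working it through.** **Inputs.** N=201, effect size 0.35, 80% power, simplest test, level 0.05, control infection rate 0.40, detectable difference 0.185 (all section 15.1); 1:1 allocation (section 10.5), so about 100.5 per arm. Assumption: effect size means a standardised mean difference d, since section 15.1 does not define it.

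**Step 1: the plan's continuous figure.** Noncentrality = d·√(n₁n₂/(n₁+n₂)) = 0.35·√(100.5·100.5/201) = 0.35·7.089 = 2.481.
- One-sided, normal approximation: Φ(2.481 − 1.645) = 79.8%. Noncentral t: 79.6%. Detectable d = (1.645 + 0.842)·√(2/100.5) = 0.351 (t: 0.352). Required N = 202 (t: 204). This matches the plan.
- Two-sided, normal approximation: Φ(2.481 − 1.960) = 69.9%. Noncentral t: 69.5%. Detectable d = (1.960 + 0.842)·√(2/100.5) = 0.395 (t: 0.397). Required N = 258 (t: 259). This does not match.

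Other two-sided readings also fail to give 80%: Wilcoxon with relative efficiency 0.955, 67.9%; 2:1 allocation, 64.8%; 201 per arm, 93.9%; 0.35 read as Cohen's f, 99.9%. With all 240 patients and no dropout, two-sided power is 77%.

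**Step 2: the section's figures for proportions.** Power = Φ[(|p₁−p₂| − z·SE₀)/SE₁], with SE₀ pooled and SE₁ unpooled.

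| Comparison | Stated power | Two-sided | One-sided |
|---|---|---|---|
| 0.40 vs 0.215, N=200 | 80% | 81.4% | 88.8% |
| 0.40 vs 0.23, N=234 | 80% | 80.3% | 88.0% |
| 0.40 vs 0.215, N=234 | 86.5% | 87.1% | 92.7% |
| 0.40 vs 0.17, N=205, level 0.005 | 80% | 80.8% | 86.6% |
| Polytomous 0.30 vs 0.49, N=202 | 80% | 79.3% | 87.3% |

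The polytomous row reads the 0.19 as an increase from 0.30, tested at an unadjusted 0.05. All five rows fit a two-sided test. The continuous figure does not.

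**Step 3: recovery time.** Take 100 evaluable patients per arm.
- No treatment effect: 0.40·100 = 40 infected in each arm. Noncentrality = 0.35·√(40·40/80) = 1.565. Noncentral t, two-sided: power about 34%, detectable d 0.63. One-sided power: 46%.
- The 0.185 difference achieved: 40 vs (0.40 − 0.185)·100 = 21.5. Noncentrality = 0.35·√(40·21.5/61.5) = 1.309. Two-sided: power about 25%, detectable d 0.76. One-sided power: 36%.

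The recovery-time shortfall therefore remains whichever sidedness was intended.

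**Step 4: hospital length of stay.** The documents give no admission rate, so no figure can be derived from them. For illustration only, if admitted patients alone were analysed: an assumed 20 admitted per arm gives a detectable d of 2.802·√(2/20) = 0.89, and an assumed 10 per arm gives 2.802·√(2/10) = 1.25 (two-sided, normal approximation).

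**The case against.** The strongest reply is that nothing has been miscalculated. The figure is correct for a one-sided 0.05 test, the objectives are directional, and the section promises two-sided testing nowhere. That stands so far as it goes: the one-sided test is inferred from the arithmetic, and a reader should not conclude that the sponsor knowingly changed convention. The defect is an unstated and apparently inconsistent sidedness within one section.

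A second reply is that CD4 and CD8 are measured at enrolment and covariates will be modelled. If covariates explained 1 − (0.35/0.397)² = 22% of the variance (a correlation of about 0.47), two-sided power at 0.35 would return to 80%. This is possible, but the plan gives no such correlation for these endpoints, and it attributes the 80% to the simplest procedure before any adjustment.

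Third, 21.5 infected in the treated arm is not an expected count. It is the control rate less the minimum detectable difference. Section 15.1 also says the infection rate may exceed 40%, which would enlarge the subset. For that reason the recovery-time result is given as a range tied to the 0.40 assumption.

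A reader might go further and apply the infected count to length of stay as well. The documents do not support that. Patients without COVID-19 can be admitted (secondary objective 2 concerns them), many infected patients may not be, and a count of overnight stays could be zero for everyone else. Scoring zeros would keep N near 200 with a heavily zero-inflated variable, but the plan does not say whether this is intended.

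Finally, these are secondary endpoints in a self-described pilot. That limits the weight of the point but does not correct the stated figures.

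**Conclusion.** The point holds in two parts.

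For continuous endpoints measured in all patients (CD4, CD8, CD4/CD8), the two-sided convention that fits the section's figures for proportions gives about 69.5% power at 0.35, roughly 10 points below the stated 80%. The unadjusted detectable effect is about 0.40 SD. This rests on reading effect size as a standardised mean difference and on inferring sidedness from reproduction.

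For recovery time, N=201 is the wrong denominator under either sidedness. At the assumed 0.40 control rate, two-sided power at 0.35 is about 25% to 34%.

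For length of stay the conclusion is narrower: the 80% claim is unsupported until the analysed population is defined, and no replacement figure follows from the documents. Nor should anyone infer that the primary-endpoint calculation is affected. It reproduces two-sided at the stated level.

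**What to change.** In section 15.1:
- State that all calculations are two-sided, at 0.05 unless another level is given, and define effect size as a standardised mean difference if that is what is meant.
- Restate the unadjusted detectable effect for CD4, CD8 and CD4/CD8 as about 0.40 SD at N=201. Claim a gain from covariate adjustment only with a stated assumed correlation. Revise the sentence that carries the justification over to counts to match.
- For recovery time, give the detectable effect as a range: about 0.63 SD (40 vs 40 infected, no treatment effect) to 0.76 SD (40 vs about 21.5 infected, if the 0.185 difference is achieved), with power of only about 34% to 25% at 0.35.
- For hospital length of stay, drop the 80% claim from N=201 and do not substitute the infected count. Say whether patients not admitted score zero. If only admitted patients are analysed, base the figure on an explicitly assumed admission rate.

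The cost is a few sentences and less favourable stated figures. Enrolment and the primary-endpoint calculation are unchanged.

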	
 6. Patients with active infectious disease requiring antibiotics 7. Patients with hospitalization within the previous 3 months for acute myocardial infarction or congestive heart failure 8. Patients with advanced malignancy receiving cytotoxic chemotherapy 9. Patients with a Karnofsky Performance Scale score of less than 60 10. Patients with prior history of solid organ (kidney, liver, heart, lung, pancreas) or bone marrow transplant 11. Patients with active autoimmune disease on immunosuppressive medication 12. Patients receiving Plaquenil 13. Participation in an investigational drug or device trial in previous 30 days 14. History of allergy or intolerance to Ta1 15. Any other medical or psychiatric condition that, in the opinion of the Investigator, would compromise patient safety or interfere with the objectives of the protocol or completion of the protocol treatment.
Drug Formulation:	Ta1 is contained, stored, and dispensed from individual tamper-proof glass vials with 1.6 mg Ta1 as a lyophilized cake containing 5% mannitol, buffered with phosphate to pH 6.4-7.3. Vials are reconstituted with 1 mL of supplied diluent (sterile Water for Injection), prior to subcutaneous administration.
Dose and Mode of Administration:	Active arm: 1.6 mg Ta1 in 1 mL SC injection twice weekly after dialysis
Duration of Treatment:	8 weeks
Reference Therapy, Dose and Mode of Administration:	Control arm: standard care
Duration of Treatment:	8 weeks
Randomization:	
Patients will be randomized 1:1
 
Randomization will be stratified by site

Efficacy Endpoints:	Primary Efficacy Endpoint

	
The primary efficacy endpoint is reduction in documented infection with COVID-19.
 
Secondary Efficacy Endpoints
 
The secondary efficacy endpoints are:
 
1. Need for hospitalization2. Hospital length of stay3. ICU admission4. ICU length of stay5. Mechanical ventilation6. Duration of mechanical ventilation7. Recovery time from COVID-198. Change in any existing comorbidities (e.g., worsening congestive heart failure) or occurrence of newly diagnosed disease9. Incidence of non-COVID-19 infections (other respiratory, urinary tract, cellulitis, etc.)10. Change in T lymphocyte subsets (CD4, CD8)11. Mortality
Safety Endpoints:	Adverse events, vital signs, and laboratory parameters

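### The ordinal power statement in section 15.1 labels a log odds ratio of 0.725 as an odds ratio, and the covariate-adjusted figures label R-squared as correlation (a lesser, conservative slip)

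*Combined protocol and SAP*

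**What the plan says.** Section 15.1 gives a separate power statement for each type of outcome.

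- **Ordinal outcome.** Assuming three categories that are equally common when the arms are averaged: "With a sample size of 200 we can detect a minimal improvement of size 0.725 in the overall odds ratio with 80% power".
- **Primary binary outcome, unadjusted.** "Assume the infection rate for the control group is about 0.40", and "a sample of size 200 will be able to detect a change at least at 0.185 in the infection rates" with 80% power.
- **Primary binary outcome, adjusted by multiple logistic regression.** "say if the correlation is 0.2, we can detect a minimal difference at 0.202 with a sample size of 200". Then: "If the correlation is 0.5, the minimum detectable difference would be 0.25".

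The significance level is 0.05 unless stated otherwise. Sidedness is not given. The synopsis says "Patients will be randomized 1:1". None of these power statements mentions a log odds ratio or an R-squared.

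**The concern.** An odds ratio of 0.725 is a modest shift, and 200 patients would not normally give 80% power for it on a three-level scale. A reader relying on section 15.1 would think the trial sensitive to such a shift. If 0.725 is really on the log scale, the trial can reliably see only about a doubling or halving of the odds.

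The adjusted figures raise a related question of scale. A correlation of 0.2 corresponds to an R-squared of only 0.04, which should hardly move the detectable difference. Yet the plan's figure goes from 0.185 to 0.202.

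**Working it through.** **Inputs.** From section 15.1: N = 200 in total, 80% power, alpha 0.05, three categories of 1/3 each, control infection rate 0.40. From the synopsis and section 10.5: 1:1 allocation. Assumed: two-sided tests, and a treated infection rate below control. The normal quantiles are 1.960 and 0.842 (sum 2.802).

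**1. Ordinal statement.** For 1:1 allocation, the proportional-odds (Whitehead) formula is

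SE(log OR) = sqrt{12 / [N(1 − Σp³)]}, with Σp³ = 3 × (1/3)³ = 1/9.

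SE = sqrt[12 / (200 × 8/9)] = 0.2598.

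Detectable log odds ratio = 2.802 × 0.2598 = 0.728, and exp(0.728) = 2.07, with inverse 0.48.

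The plan's figure reproduces with 0.725 on the log scale: power = Φ(0.725/0.2598 − 1.960) = 79.7%, and the N needed for 80% is 12 × 7.849 / (0.725² × 0.889) = 201.6. Readings on the odds-ratio scale, with the same formula:

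| Reading of 0.725 | abs. log OR | Power, N = 200 | N for 80% |
|---|---|---|---|
| Log odds ratio | 0.725 | 79.7% | 202 |
| OR 0.725 (or 1.38) | 0.322 | 23.5% | 1,025 |
| OR 1.725 (0.725 above 1) | 0.545 | 55.5% | 356 |
| OR 0.275 (0.725 below 1) | 1.291 | 99.9% | 64 |

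Simulating the tie-corrected Wilcoxon test (20,000 runs, 100 per arm) gave 79.2%, 23.4%, 54.9% and 99.8% in the same order. One-sided tests do not help: OR 0.725 gives 34.2% and OR 1.725 gives 67.5%.

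**2. Adjusted binary figures.** The usual inflation replaces N by N(1 − R²), where R² is from regressing treatment on the other covariates. Detectable differences below 0.40 at N = 200 and 80% power, under two standard formulas:

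| R² | Pooled two-proportion | Wald on log OR | Plan |
|---|---|---|---|
| 0 | 0.182 | 0.185 | 0.185 |
| 0.04 (r = 0.2) | 0.185 | 0.189 | |
| 0.05 | 0.186 | 0.190 | |
| 0.20 | 0.201 | 0.206 | 0.202 |
| 0.25 (r = 0.5) | 0.207 | 0.212 | |
| 0.50 | 0.248 | 0.258 | 0.25 |

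The plan's 0.202 and 0.25 sit on the R² = 0.2 and 0.5 rows under the pooled formula. Power there is 80.3% with 80 per arm and 80.9% with 50 per arm. If 0.2 and 0.5 were correlations, the effective sizes would be 96 and 75 per arm, and power at the stated differences would be 87.0% and 93.7%.

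One coincidence was checked. If the treated rate is taken to be higher than 0.40, r = 0.2 gives 0.201. That direction then fails at r = 0.5 (0.227 against 0.25) and unadjusted (0.197 against 0.185).

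**3. Size of R² under randomisation.** With k baseline covariates as main effects, chance alone gives an expected R² of about k/(N − 1). For an assumed k = 10 this is 10/199 = 0.05. The detectable difference then grows by 0.186 − 0.182 = 0.004 (pooled) or 0.190 − 0.185 = 0.005 (Wald).

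**The case against.** **The sentence does not strictly say that the odds ratio is 0.725.** It speaks of an improvement of that size in the odds ratio, which could mean 1.725. This stands: a reader might infer a flat 24% power, but the wording does not fix that reading, and about 55% is as defensible. It does not rescue the sentence, because neither value is near 80%, and the remaining reading (0.275) gives almost 100%.

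**Nothing in the design hangs on it.** This largely stands. Section 15.1 presents 240 patients as a choice made for a pilot. Section 8.2 defines no secondary endpoint as a three-level scale, and section 15.2 plans multinomial regression for such outcomes without naming a proportional-odds model. Correcting the label changes no sample size, endpoint, test or decision rule.

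**The correlation wording is loose and errs on the safe side.** This also stands. Read as correlations, the plan under-claims its power. The two slips run in opposite directions and should not be merged into one charge of overstated power.

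**Randomisation does not rule out a large R².** A reader might infer that the 0.202 to 0.25 penalty can never apply here. Section 15.2 does not support that, because it plans treatment-by-covariate interactions. Take a balanced binary covariate and an uncentred product term. Treatment is fully determined where the covariate is 1 and unexplained where it is 0, so residual variance is 0.5 × 0.25 = 0.125 out of 0.25, and R² = 0.50. The treatment coefficient in that model is a subgroup effect, but the case exists. The small-R² statement must be limited to main-effects models.

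**Conclusion.** The ordinal power statement is wrong as written. At N = 200, 80% power corresponds to a common odds ratio of about 2.07 or 0.48. Taken as an odds ratio, 0.725 has about 24% power and 1.725 about 55%. This assumes proportional odds, three equal categories and a two-sided test; on the log scale a one-sided test would give 87% power, so two-sided is what matches the plan's 80%.

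The correlation label is a secondary, conservative error: the figures are right for R-squared.

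A reader might infer that the primary power claim falls too. It does not: 0.185 at N = 200 has 80.0% power by the Wald formula and 81.4% by the pooled one. Severity is moderate to minor, since this is a labelling error on a secondary outcome type in a pilot.

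**What to change.** In section 15.1:

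1. Replace the ordinal sentence with: with N = 200, there is 80% power for a common odds ratio of about 2.07 (or 0.48), i.e. a log odds ratio of about 0.73, two-sided 0.05.
2. Relabel the values 0.2 and 0.5 as the R-squared of treatment on the other covariates.
3. Add that, in a main-effects model with baseline covariates, 1:1 randomisation makes the expected R-squared small, so the detectable difference stays close to the unadjusted one: about 0.004 to 0.005 larger at an assumed R-squared of 0.05.

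Use one formula throughout. In particular, do not put 0.186 beside the retained 0.185: the first is from the pooled formula, the second matches the Wald formula, and the pair would suggest that adjustment costs only 0.001.

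The cost is a few sentences of text, with no effect on sample size, conduct or data. The stated ordinal sensitivity will look less favourable to anyone who read 0.725 as an odds ratio.
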